5.3 Exploratory Endpoints

N/A.

5.4 Safety Endpoints

Safety endpoints are as follows:

- Incidence of AEs,
- Incidence of AEs by severity,
- Incidence of AEs by relationship to knee implant (study device),
- Incidence of AEs by relationship to NAVIO System,
- Incidence of AEs that led to discontinuation,
- Incidence of AEs by outcome,
- Incidence of serious adverse events (SAEs),
- Incidence of adverse device effects (ADE),
- Incidence of serious adverse device effects (SADEs),
- Incidence of unanticipated adverse device effects (UADEs),
- AEs of special interest,
- Listing of revisions and details of components removed during revision.

6. Statistical Considerations

CONFIDENTIAL AND PROPRIETARY

This document contains information that is confidential and proprietary to Smith & Nephew PLC and Smith & Nephew, Inc. and is intended for use only by Smith & Nephew and its manufacturer. It shall not be reproduced or copied in whole or in part, nor shall the contents be disclosed by any means without prior written permission from Smith & Nephew, nor shall anyone make any use of it that is contrary to the expressed or implied wishes of Smith & Nephew.

Statistical Analysis Plan	 smith&nephew
A Retrospective Study of the NAVIO Robotic-assisted Surgical System	Number: 16-NPFS-11
	Version: Final 1.0, Jan 29, 2018
	Page: 12 of 25

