**Protocol Synopsis:**

Title of Study:	A Retrospective Study of the Navio ◊ Robotic-assisted Surgical System
Study Type:	Post-market
Study Device:	Navio ◊ Robotic-assisted Surgical System
Indications	Navio System-assisted Unicondylar Knee Replacements (UKR) are indicated for restoring either compartment of a knee that has been affected by: 
 
• Non-inflammatory degenerative joint disease including osteoarthritis, traumatic arthritis, or avascular necrosis
 
• Correction of functional deformity
 
• Treatment of fractures that are unmanageable using other techniques
 

Study design:	A retrospective, multi-center, cohort study with prospective follow-up and comparison to historical control
Primary Endpoint:	Navio System assisted Unicondylar Knee Replacement (UKR) revision rate 2 years postoperative
Secondary Endpoints:	Given the retrospective-prospective study design, secondary endpoint data will be collected to the extent that it is available and will include: 
 
• Change in Knee Society Score (KSS) from baseline to 2 years (-3months) or greater postoperative
 
• Change in VR12 from baseline to 2 years (-3months) or greater postoperative
 
• Anterior/Posterior and lateral radiographic assessments
 

Safety Assessment:	Study device and procedure-related adverse events (AE) incidence and frequency
Length of Study:	Up to 1 year: includes enrollment phase and collection of a minimum of 2-year postoperative follow-up data
Study Visits:	Retrospective pre-operative, operative and any available postoperative follow-up; Prospective 2-year or greater postoperative follow-up
Number of Sites:	Up to 10 sites in the United States and Europe
Sample Size:	One hundred twenty-eight (128) subjects, including 10% inflation to allow for attrition
Inclusion Criteria:	
 
1. Male or female subjects ≥18 years old (at the time of surgery) who have undergone Navio System-assisted UKR prior to IRB/EC site approval. This includes UKR procedures with all Unicondylar Knee cemented implant designs.
 
2. Subject had a primary diagnosis of unicompartmental, non-inflammatory degenerative joint disease including osteoarthritis, traumatic arthritis, or avascular necrosis, required correction of functional deformity, or required treatment of fractures that were unmanageable using other techniques.
 

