## **8. SAFETY REPORTING**

Adverse Events (AE) related to the study device (Navio), the unicondylar implant, or procedure including Adverse Device Effects (ADE), Serious Adverse Device Effects (SADE), Unanticipated Serious Adverse Device Effect (USADE), and Device Deficiencies (DevD) occurring from the time of the study procedure until revision or study completion must be recorded on the appropriate CRF and reported. If the event is known to have been previously reported to Smith & Nephew, this must be noted on the CRF. After consent, in addition to all events related to Navio, the unicondylar implant or the procedure, all serious adverse events (SAE), regardless of causality, must be recorded on the appropriate CRF and reported to sponsor and IRB if necessary. Events leading to a revision should be reported at all times regardless of causality.

Adverse Device Effects (ADE) occurring after study completion will be handled as product complaints reportable by the Sponsor and will not be entered into the study database.

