#### **F. Device Deficiency (DevD)**

A DevD is an inadequacy of a medical device with respect to its identity, quality, durability, reliability, safety, or performance. DevD include malfunctions, use errors, and inadequate labeling.

For this study, DevD should be reported when they concern any component of the Navio system as well as its packaging and tools that need to be used during surgery according to the User Manual.

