#### **8.2. Safety: Investigator's Responsibilities**

##### Reporting of adverse events during the retrospective data collection portion of the study:

Investigators are responsible for documenting ADE, SADE, U(S)ADE and DevD identified during the medical record review. This includes events related to the study device (Navio), the unicondylar implant, or procedure. Investigators will record ADE, SADE, U(S)ADE and observed DevD, together with an assessment in the subject's source data. Investigators are responsible for documenting ADE, SADE, U(S)ADE and DevD on the appropriate CRF and submitting them to the Sponsor according to the timelines described.

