##### Reporting of adverse events during the prospective data collection portion of the study:

At each prospective contact with the subject, the Investigator must seek information on previous events and current events that could be deemed serious by specific questioning and, as appropriate, by assessment of the subject. All study device (Navio), unicondylar implant, and procedure related adverse events and all serious adverse events (SAE) regardless of causality, must be recorded on the appropriate CRF and reported to sponsor and IRB. Unresolved AE should be followed by the Investigator until the events are resolved or through to the end of the study, whichever occurs first. Unresolved AEs at the end of the subject's participation should be monitored by the Investigator as part of the site's normal standard of care.

All events must be recorded in standard English medical terminology.

The Investigator will categorize AE as mild, moderate or severe based on the following definitions:

- Mild: the subject is aware of the sign or symptom, but finds it easily tolerated. The event is of little concern to the subject and/or little clinical significance. The event is not expected to have any effect on the subject's overall health or well-being.
- Moderate: the subject has discomfort enough to cause interference with or change in usual activities. The event is of some concern to the subject's health or wellbeing and may require medical intervention and/or close follow-up.
- Severe: the adverse event interferes considerably with the subject's usual activities. The event is of definite concern to the subject and/or poses a substantial risk to the subject's health or wellbeing. The event is likely to require medical intervention and/or close follow-up and may be incapacitating or life threatening. Hospitalization and treatment may be required.

The Investigator is responsible for describing the relationship of the AE to the study device/procedure based on the following definitions:

- Unrelated: the event is clearly not related to the study device or procedure
- Possible: the event may or may not be related to the study device or procedure. A relationship cannot be ruled out.
- Definite: the event is clearly related to the study device or procedure.

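### The SAP labels the knee implant the study device and plans no procedure-related, combined device-or-procedure or stand-alone device-deficiency output, although it does tabulate AEs related to Navio

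*SAP*

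**What the plan says.** **Protocol.** The synopsis defines the safety assessment as "Study device and procedure-related adverse events (AE) incidence and frequency". Section 8 requires recording of "Adverse Events (AE) related to the study device (Navio), the unicondylar implant, or procedure", so Navio is the study device and the implant and the procedure are two further categories. Section 8.2 repeats this for the record review: "This includes events related to the study device (Navio), the unicondylar implant, or procedure". Section 8.1 F adds device deficiencies: "For this study, DevD should be reported when they concern any component of the Navio system". For prospective follow-up, section 8.2 makes the investigator responsible for "describing the relationship of the AE to the study device/procedure based on the following definitions". The lowest level of that scale reads "Unrelated: the event is clearly not related to the study device or procedure", so the wording joins device and procedure in one statement. Section 9.4 plans numbers, types and rates of AEs. It names neither a breakdown by relationship nor a table of device deficiencies.

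**SAP.** Section 5.4 lists "Incidence of AEs by relationship to knee implant (study device", and its next item is AEs by relationship to the NAVIO System. Section 7.13 plans subject counts by worst relatedness to the investigational device and, as a separate item, by worst relationship to the NAVIO device, together with SAEs, ADEs, SADEs and UADEs. Neither section mentions relationship to the procedure or device deficiencies. Section 7.15 lists two changes from the protocol: the full analysis set is dropped, and change from baseline in KSS and VR-12 is replaced by 24-month summaries. Neither concerns safety.

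**The concern.** The safety measure that the protocol puts in its synopsis has no matching output in the SAP. A reader of the study report who looks for the proportion of subjects with a device- or procedure-related event would not find it, and could not build it from the tables that are planned.

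The terms make this worse. A table headed *study device* would refer to Navio under the protocol and to the implant under SAP 5.4. Navio is a tool for preparing bone, so whether an event is attributed to the system, to the prosthesis or to the operation is the distinction a safety reader will want. Device deficiencies are the most direct record of how the system performed, and those that harmed nobody would be collected without any planned report.

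**Working it through.** No figure is in dispute and the documents give no event counts, so the check sets the texts side by side.

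**1. Terms and outputs**

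| Item | Protocol | SAP 5.4 | SAP 7.13 |
|---|---|---|---|
| Meaning of *study device* | Navio (sections 8, 8.2) | Knee implant | Term not used; *investigational device*, undefined |
| AEs related to Navio | Recorded | Tabulated | Tabulated |
| AEs related to the implant | Recorded | Tabulated | Tabulated, if *investigational device* means the implant |
| AEs related to the procedure | Recorded; named in the synopsis | None | None |
| Device-or-procedure-related, combined | Synopsis safety assessment | None | None |
| Device deficiencies | Recorded (sections 8, 8.1 F) | None | None |

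Of the three relationships the protocol names, the SAP tabulates two. The detailed tables in 7.13 follow the criteria of its overall table, so they add no procedure category.

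**2. Whether the combined incidence follows from the planned tables.** Let N, I and P be the sets of subjects with at least one AE related to Navio, the implant and the procedure, and T the set with any recorded AE. The SAP reports |N|, |I| and |T|. Under the protocol's terms the synopsis measure is |N ∪ P|. With the implant included, as in section 8, it is |N ∪ I ∪ P|. The planned tables give only bounds:

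- |N| ≤ |N ∪ P| ≤ |T|
- max(|N|, |I|) ≤ |N ∪ I ∪ P| ≤ |T|

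Subjects whose only related event is procedural lie in the gap. If the label is read as in SAP 5.4, the synopsis phrase becomes |I ∪ P|, a different quantity. This is why the label matters.

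**3. Whether T can stand in.** Protocol section 8 has three recording rules: (a) events related to Navio, the implant or the procedure, throughout; (b) events leading to revision, whatever the cause, throughout; (c) after consent, all SAEs, whatever the cause. Under section 5.2, subjects who have completed a 2-year visit, have died or are lost to follow-up may enter under a waiver. For them there is no consent to trigger rule (c). T is therefore close to the related set in waiver subjects and wider in consented subjects, in proportions set by the consent route. The documents do not give that split.

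**4. Device deficiencies.** Section 8.1 C counts an AE that results from malfunction or use error as an ADE, and the SAP tabulates ADEs, SADEs and UADEs. The gap is therefore the deficiencies that caused no AE. The protocol gives these some weight: section 8.3 sets a 24-hour report for those that could have led to a SADE, and section 8.4 has the sponsor consider whether the risk analysis needs updating.

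**5. What the ADE counts cover.** Section 8.1 C ties an ADE to the investigational medical device and adds events related to the sponsor's own unicondylar implant. The SAP defines neither *investigational device* nor ADE, so the scope of its ADE, SADE and UADE counts is not stated.

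**6. Grades.** The scale in protocol 8.2 is worded jointly for device or procedure. SAP 5.4 needs at least separate Navio and implant grades. Under the protocol wording alone, a *definite* grade does not show which of them is meant.

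**The case against.** The strongest defence is that nothing is lost from the data. Procedure-related events are recorded and count in overall AE incidence and in the severity, outcome and, where serious, SAE tables. The synopsis asks for a pooled measure, not a separate procedure table, and for retrospective data the overall incidence comes close to it. Protocol 9.4 asks for no breakdown by relationship and no deficiency table, so on relationship the SAP already goes beyond 9.4. SAP 7.5 also summarises intra-operative complications. The label in 5.4 occurs once, beside the words knee implant, so a programmer would know which table to build. And 7.15 is about changes in analysis methods, of which 9.4 specified none on these points.

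Most of this stands as a limit on the point. A reader might infer that the SAP produces no safety assessment of Navio. It does: AEs by relationship to Navio appear in both 5.4 and 7.13. A reader might also infer that malfunction harms vanish, but those that cause an AE are ADEs and are tabulated. Nor can one conclude that the joint grade in 8.2 makes separate tables impossible. The SAP is written to CRF version 3.0, which is not among the documents and may hold separate fields. The grading text also stands under the prospective heading and does not say that each event receives only one grade.

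The defence does not supply the synopsis measure. Overall incidence includes all-cause SAEs after consent, so it approximates that measure only in subjects outside that rule.

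**Conclusion.** The point holds as a gap in planned safety output, together with a conflict of terms. Followed as written, the SAP yields Navio-related and implant-related AE incidence. It does not yield procedure-related incidence, the combined device-or-procedure-related incidence named in the synopsis, or any account of Navio deficiencies that caused no AE. The omission from 7.15 is a lapse in transparency, not a misstatement.

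One of three named relationships is untabulated. The numerical effect depends on how many subjects had only procedure-related events and how many consented subjects had unrelated SAEs, neither of which is given. The primary endpoint and its non-inferiority test are unaffected. The point should be corrected, but it does not threaten the main result.

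It assumes that *investigational device* in 7.13 means the implant, which is the natural reading because it is listed apart from the NAVIO device. If it means something else, the implant table in 7.13 is also in doubt. The grading mismatch is conditional on the CRF and carries no weight in this conclusion.

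**What to change.** In SAP 5.4 and 7.13:

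- Use three fixed terms throughout (Navio System, unicondylar implant, procedure). Drop *study device* and *investigational device* from table titles, or define them as the protocol does.
- State which of the three the ADE, SADE and UADE counts cover.
- Add AE incidence by relationship to the procedure.
- Add the combined device-or-procedure-related incidence, stating whether the implant is included.
- Add a count and listing of Navio device deficiencies, whether or not they led to an AE.
- Record these additions in 7.15.

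Check CRF version 3.0 before touching the protocol. If it already records relationship separately for Navio, implant and procedure, only the SAP changes. If it holds a single joint grade, reconcile protocol 8.2 with the separate grades the tables need.

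The cost is a few extra tables and one listing and, at most, a re-query of relatedness for AEs already entered.

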6.1 Determination of Sample Size

The sample size obtained for study is based on the non-inferiority of the percent of revision-free survival expected to be obtained at 2 years in the study, π to one obtained from existing literature, π_0 . The Australian Orthopaedic Association National Joint Replacement Registry 2015 Annual Report (1) indicates that the revision-free survival at 2-years is 95.7%.

Using a non-inferiority margin, δ of 7%, a sample size of 115 subjects would provide at least 80% power at the 5% significance level using the exact binomial method. To allow for a 10% attrition and drop-out rate, a total of approximately 128 subjects would be enrolled into the study.

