#### **9.1. Sample Size Calculation**

This study will screen and consent patients until a total of 128 subjects, from up to 10 sites, treated with the study device have been enrolled in the study.

The study is intended to test for non-inferiority in the percentage of revision-free survival at 2 years recorded during the study compared to existing literature. The Australian Orthopaedic Association National Joint Replacement Registry 2015 Annual Report (13) records the revision-free survival for at 2-years as 95.7%.

Using a non-inferiority margin of 7%, a sample size of 115 subjects will provide at least 80% power at the 5% significance level using exact binomial methods. To allow for a 10% attrition and drop-out rate, a total of 128 subjects will be enrolled.

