#### **9.2. Missing Data**

A complete accountability report, along with the explanation for lost-to-follow-up, death, revision, and withdrawn subjects is to be provided in the Clinical Study Report (CSR). The methods used to handle missing or incomplete data for the efficacy and safety measures will be detailed in the Statistical Analysis Plan (SAP).

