### **9.4. Analyses**

A formal SAP will be written and finalized prior to database lock. The SAP will detail the summaries and analyses to be performed.

- Primary endpoint:

The primary endpoint of the study is the Navio System assisted UKR revision rate at 2 years postoperatively. A one-sided 95% confidence interval for the revision [free] rate of the Navio System assisted UKR will be calculated using exact binomial methods. Non-inferiority, using a 7% non-inferiority margin will be declared if the lower bound of the confidence interval is  $>88.7\%$ . Time to occurrence of revision will also be analyzed using Kaplan-Meier survival analysis. Where appropriate, statistical modeling will be considered with prognostic and baseline factors adjusted for.

- Secondary endpoints:

Where appropriate, the secondary endpoints will be analyzed using either an ANOVA or Repeated Measures analysis, depending on whether a comparison between two time points or multiple time points is conducted. In each case, prognostic and baseline factors will be adjusted for. For endpoints where further analysis is not warranted, or not considered appropriate, tabulations detailing frequency distributions and/or summary statistics will be produced.

- Safety:

Numbers and types of AE, along with rates of AE types; with 95% confidence intervals for the rates (constructed using either exact binomial or asymptotic methods where appropriate) will be tabulated.

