7.10 Analysis of Primary Endpoint

CONFIDENTIAL AND PROPRIETARY

This document contains information that is confidential and proprietary to Smith & Nephew PLC and Smith & Nephew, Inc. and is intended for use only by Smith & Nephew and its manufacturer. It shall not be reproduced or copied in whole or in part, nor shall the contents be disclosed by any means without prior written permission from Smith & Nephew, nor shall anyone make any use of it that is contrary to the expressed or implied wishes of Smith & Nephew.

Statistical Analysis Plan	smith&nephew
A Retrospective Study of the NAVIO Robotic-assisted Surgical System	Number: 16-NPFS-11
	Version: Final 1.0, Jan 29, 2018
	Page: 20 of 25

For the primary endpoint, cumulative proportion (or percentage) of subjects with implant survivorship at 2+ years (96 weeks), the following is the hypothesis would be performed:

H_0 (null): $S(t) = \pi \leq (\pi_0 - \delta)$ versus

H_a (alternate): $S(t) = \pi > (\pi_0 - \delta)$,

where π = expected percentage of subjects with implant survivorship at 2 years, π_0 = historical control implant survivorship (95.7%) and δ = margin of non-inferiority (7%).

Because not all subjects would be fully evaluated through study completion, the Kaplan-Meier product limit survival estimate would be used to estimate implant survivorship, $S(t)$ where $S(t)$ is the proportion of subjects at time t , without a device revision. Time to implant revision would be the endpoint of interest in the determination of implant survivorship.

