Cumulative proportions of subjects with implant survivorship at 2 years would be calculated and displayed accordingly. Subjects who complete the study without a revision would be censored at their last known date in the study. A subject who prematurely discontinues from study as a result of death or for any other reason would be censored at the date this event occurred. A subject who is lost to follow-up would be censored at the last known contact date. The Kaplan-Meier estimate for implant survivorship would be presented with the corresponding two-sided 95% Confidence Intervals (CIs). This study's hypothesis test would only be carried out at the end of the study at 2+ years (96 weeks). From this test, if the lower limit (LL) of the 95% two-sided CI for $S(t = 2 \text{ years}) > (\pi_0 - \delta) = 88.7\%$, then H_0 will be rejected in favor of H_a (i.e. demonstration of non-inferiority of the investigational device) otherwise H_0 would not be rejected. Kaplan-Meier estimates for implant survivorship would also be non-inferentially estimated at the intermediate time points of 6 months (24 weeks), 1 year (48 weeks), and at 18 months (72 weeks) as well as subsequently at 30 months (120 weeks).

The primary endpoint would be analyzed using the safety population as the primary analysis population while the per protocol population would be used for sensitivity analysis.

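### SAP 7.10 replaces the protocol's primary success rule without listing the change or naming the interval scale, while SAP 6.1 keeps a power statement that is correct only for the protocol rule

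*SAP*

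**What the plan says.** **Protocol.** Section 9.1 plans 115 evaluable and 128 enrolled subjects, and claims that "a sample size of 115 subjects will provide at least 80% power at the 5% significance level using exact binomial methods". Section 9.4 gives the matching test: "A one-sided 95% confidence interval for the revision [free] rate of the Navio System assisted UKR will be calculated using exact binomial methods", with non-inferiority declared if the lower bound exceeds 88.7%. Kaplan-Meier appears there only as an additional analysis. Section 9.2 adds that "The methods used to handle missing or incomplete data for the efficacy and safety measures will be detailed in the Statistical Analysis Plan".

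**SAP.** Section 6.1 repeats the protocol's power claim almost word for word: "a sample size of 115 subjects would provide at least 80% power at the 5% significance level using the exact binomial method". In section 7.10, however, "the Kaplan-Meier product limit survival estimate would be used to estimate implant survivorship", because some subjects will not be followed to the end. The null hypothesis is rejected "if the lower limit (LL) of the 95% two-sided CI for" two-year survivorship lies above 88.7%. No transformation or variance formula is given. Section 7.15, which records departures from the protocol, has two entries: the dropped full analysis set, and the replacement of change from baseline in KSS and VR-12 by 24-month summaries. The primary test is not among them.

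**The concern.** This is the trial's only hypothesis test, and the two documents decide it by different rules. The estimator changes from a binomial proportion to Kaplan-Meier, and the lower-tail level changes from 5% to 2.5%. The first change has a stated reason and the second has none. With so few revisions expected, the choice of interval scale moves the pass mark by one revision, and the SAP leaves that choice open. A reader of SAP 6.1 would take the power and error rate there to describe the planned test, when they describe the protocol's test.

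**Working it through.** **Inputs.** Historical survivorship 95.7%, also taken as the true rate for power; margin 7 points; threshold 95.7% − 7% = 88.7%; n = 115 evaluable (Protocol 9.1, SAP 6.1). Enrolment: 115/0.9 = 127.8, so 128. Greenwood variance is my assumption, since the SAP names none.

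**1. Reproduce the plan's figure (protocol rule).** Let X be the number of revisions: X ~ Bin(115, 0.043) at 95.7% survivorship and Bin(115, 0.113) at the 88.7% boundary. The one-sided 95% Clopper-Pearson lower limit L solves P(X ≤ x | revision probability 1 − L) = 0.05.
- x = 7: L = 0.8887, pass. x = 8: L = 0.8780, fail.
- Power = P(X ≤ 7 | 0.043) = 0.877. Type I error = P(X ≤ 7 | 0.113) = 0.0446.

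The claim of at least 80% power at 5% holds for this rule.

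**2. SAP rule, 115 fully followed.** The Kaplan-Meier estimate is then S = (115 − x)/115, with SE = √(S(1 − S)/115). At x = 7, S = 0.9391 and SE = 0.0223.
- Linear: S − 1.96·SE = 0.9391 − 0.0437 = 0.8954, pass. At x = 8 the limit is 0.8839, fail.
- Log-log: S^exp(1.96·SE/(S·|ln S|)) = 0.9391^exp(0.741) = 0.9391^2.098 = 0.8766, fail. At x = 6 the limit is 0.8876, pass.

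| Rule, n = 115, complete follow-up | Most revisions allowed | Power | Type I error |
|---|---|---|---|
| Protocol 9.4, one-sided 95% exact | 7 | 87.7% | 4.5% |
| SAP 7.10, two-sided 95%, log-log | 6 | 77.4% | 2.0% |
| SAP 7.10, two-sided 95%, linear | 7 | 87.7% | 4.5% |

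The probability of exactly 7 revisions at 95.7% survivorship is 0.103. With all 128 fully followed, log-log limits allow 7 revisions (power 81.3%, type I error 1.9%).

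**3. SAP rule with the plan's own attrition.** Simulation with 128 enrolled, 10% lost uniformly over 730 days, constant hazard and the test at day 730. The ranges cover two separate simulations (13 subjects lost, or each subject lost with probability 10%).
- Two-sided 95% log-log: power about 73%, type I error 1.2% to 1.4%.
- Two-sided 95% linear: power 91% to 92%, type I error 5.7% to 5.9%.

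**4. Completers censored early.** SAP 7.3 censors unrevised subjects at their last visit, and Protocol 3 accepts a two-year visit up to 3 months early. Suppose 25%, 50% or 75% of completers are last seen in those 3 months (assumed shares). Log-log power is then 73%, 70% or 69%. Linear type I error is 5.8%, 5.8% or 6.5%.

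**5. The protocol's level with Kaplan-Meier.** Using the lower limit of a 90% two-sided log-log interval, the simulations of steps 3 and 4 (early-visit shares 0% to 75%) give power of 82% to 86% and type I error of 3.3% to 4.2%.

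**6. Evaluation time.** SAP 7.10 says the "hypothesis test would only be carried out at the end of the study at 2+ years (96 weeks"), yet writes the decision rule for t = 2 years. Ninety-six weeks is 96 × 7 = 672 days. Under constant hazard, survivorship of 0.887 at day 730 corresponds to 0.887^(672/730) = 0.895 at day 672, so a literal 96-week reading would favour the device.

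**The case against.** Much of the change has a documented basis. SAP 7.10 explains the use of Kaplan-Meier, Protocol 9.4 already planned it as an added analysis, and Protocol 9.2 leaves missing-data methods to the SAP. Two-sided 5% testing is the general default in Protocol 9 and SAP 7.1. Hypotheses, benchmark, margin and threshold are unchanged, and for a fixed method the two-sided level is the stricter one. All of this stands. But Protocol 9.4 expressly overrides the default for the primary endpoint, and nothing explains the return to two-sided limits.

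The effect is also narrow. At n = 115 with complete follow-up, the rules part only at exactly 7 revisions. Part of the fall from 77% to 73% is discreteness: log-log power with complete follow-up is 77.4% at n = 115, 74.1% at 120 and 82.4% at 126. The 69% to 70% figures depend on assumed visit timing. These limits are accepted.

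Several stronger readings are tempting, but the documents do not support them:
- *SAP 6.1 contains an arithmetic error.* It does not; its figure reproduces for the protocol rule.
- *Power is certainly lost.* With linear limits it is not; the weakness there is type I error once subjects are lost.
- *The test will be run at 96 weeks.* The SAP labels its other time points "6 months (24 weeks), 1 year (48 weeks), and at 18 months (72 weeks) as well as subsequently at 30 months (120 weeks"), all at 4 weeks per month, so this is probably shorthand.
- *The rule was changed after revision data were seen.* SAP 7.15 mentions 27 subjects in interim analyses, but reports only their missing baseline KSS and VR-12.
- *Enrolment must rise to the fully followed requirement divided by 0.9.* Kaplan-Meier uses the follow-up of lost subjects, so that division does not apply.

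**Conclusion.** The inconsistency is real. The primary success rule in SAP 7.10 differs from Protocol 9.4 in estimator and confidence level, its interval scale is open, the change is missing from SAP 7.15, and SAP 6.1 describes the other rule. The claim of at least 80% power at the 5% level is therefore not assured for the test that will be run. On the log-log scale the power part fails at n = 115 (77.4%) and, under uniform 10% loss and constant hazard, at 128 enrolled (about 73%). On the linear scale power is ample, but under the same loss the type I error is about 6%, above the stated 5%. At exactly 7 revisions in 115, an outcome with about a 10% chance at 95.7% survivorship, the conclusion turns on the unstated scale. The complete-follow-up results are exact given Greenwood variance; those with loss depend on the assumed loss and hazard patterns. The 96-week label is a secondary matter of wording.

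**What to change.** - **SAP 7.10:** state one rule, giving estimator, confidence level, interval scale, variance formula and a single evaluation time in days for two years, in place of the 96-week label.
- **SAP 7.15:** list the change of estimator and the change of confidence level, with the reason for each.
- **SAP 6.1:** restate the power for the chosen rule with its assumptions. For two-sided 95% log-log Kaplan-Meier limits this is 77% with 115 fully followed, 81% with 128 fully followed, and about 73% with 128 enrolled and 10% lost; it is lower if many completers are censored before day 730.
- **Alternative:** keep the protocol's one-sided 95% level with log-log Kaplan-Meier limits (a 90% two-sided interval), which gives about 82% to 86% power and 3% to 4% type I error under the same assumptions.

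The cost is text in three SAP sections. A protocol amendment is not essential if SAP 7.15 records the departure, and no extra subjects are needed if the restated power is accepted. The drawback of the two-sided 95% log-log rule is that the stated power becomes less favourable.
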